8.3 Clinical Examination of the Ears

A clinical examination of ears will be performed at screening. Overall results will be recorded as Normal, Abnormal Not Clinically Significant, or Abnormal Clinically Significant.

The frequency and relative frequency of the overall assessment of the clinical examination will be summarized for screening visit by treatment group.

Clinical examination results will be listed.

8.4 Pregnancy Test

A pregnancy test (serum/urine) will be performed in female subjects of childbearing potential at screening. Pregnancy test results will be listed.

9 INTERIM ANALYSIS

A sponsor blinded interim analysis focused on the primary endpoint after 33% of the officers have completed participation in the study (22 in each group). The independent programmer will prepare the dataset using a pre-prepared SAS code and will freeze them for the interim analysis. To ensure the double blinding of the study the subjects will not be presented in the assigned groups. The blinded statistician will estimate the overall proportion of PTS positive subjects in each group. Then one-sided Fisher's exact test will be used to compare the proportion of subjects with PTS positive in ZNS group with the proportion of patients with PTS positive in the placebo group. Then one-sided p-value (p_i) from Fisher's Exact Test will be converted to a z-value using the inverse Normal transformation [1,2], i.e. $z_i = \Phi^{-1}(1 - p_i)$, where $\Phi^{-1}(\cdot)$ represents the inverse standard Normal cumulative distribution function.

With 33% information, the trial would be stopped for futility if the interim z-value ≤ 0.5233 corresponding to a conditional power less than 10%. This design would provide 79.4% overall power (i.e. the probability of passing futility and reaching $p < 0.025$ for the comparison in the final analysis would be 79.4%).

Based on interim analysis the following actions may be taken:

- Stop the trial for futility
- Continue the trial as planned.

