## 12.4 Interim analysis

A sponsor blinded interim analysis focused on the primary endpoint after 33% of the officers have completed participation in the study (22 in each group). The independent programmer will prepare the dataset using a pre-prepared SAS code and will freeze them for the interim analysis. To ensure the double blinding of the study the subjects will not be presented in the assigned groups. The blinded statistician will estimate the overall proportion of PTS positive subjects in each group.

With 33% information, the trial would be stopped for futility if the interim z-value  $\leq 0.5233$  ( $p=0.60$  2-sided) corresponding to a conditional power less than 10%. This design would provide 79.4% overall power (i.e. the probability of passing futility and reaching  $p<0.025$  for the comparison in the final analysis would be 79.4%).

Based on interim analysis the following actions may be taken:

- Stop the trial for futility
- Continue the trial as planned.

Early stopping rule related to serious adverse events: In the event of a serious adverse event, DSMB will evaluate the association of the serious adverse events with the study arm, break the blind if needed, and if found to be associated with treatment, DSMB will consider the study for revision or stopping.

***Serious feasibility or design difficulties.*** If one year after the start of the trial, <50% of the planned accrual goals are met, DSM and study team will discuss difficulties in recruitment. Amount of remuneration will be revised, if needed. If there are not enough officers meeting inclusion/exclusion criteria, then the criteria will be revised without impacting study objectives. If there are recruitment difficulties, the DSM will discuss with the PI and research team what are the main reasons for these difficulties and will identify ways to deal with them. For example, if there are not enough police officers identified with a TTS  $\geq 10$ dB, then the study inclusion criteria will be revised to include members of the Bomb squad. In order to preserve the balanced design and group representation, a stratified randomization strategy will be employed. If there are difficulties in recruitment related to length of

audiometric testing pre- and post-shooting, then the DSM and research team will discuss using OAE testing.

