2.5 Treatment Assignment and Blinding

The study will be “masked” or “blinded” in the sense that all the study subjects and the study team members will be blinded to the assignment in the study groups. Only the pharmacist who will prepare the study drug kits and the unblinded statistician will have access to the kit assignments. The Medical Monitor will be contacted. A copy of the randomization list with study ID assignments will be saved in a limited access folder on a secure network server at Pharm-Olam. The Medical Monitor will be contacted in emergent medical cases when knowing the treatments assignment is mandatory for clinical care of the study subject.

The data will be presented without having the treatment assignments of individual study subjects made known to study team members including the study PI. Table shells will be blinded. If DSMB members find any safety issues, they may request specific unblinded data. Table shells for DSMB (content and formats) will be agreed upon prior to start of study.

Subjects will receive one time dose of oral ZNS or matching placebo after training if TTS is identified on audiogram 5-30 minutes after shooting. Subjects will be instructed to take study drug without food. We will recommend that capsules be swallowed whole per the current approved labeling.

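### The futility look is given to a blinded statistician with officers not shown by arm, but its rule is a directional test of ZNS against placebo that needs arm identity

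*SAP*

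**What the plan says.** SAP section 9 places the look "after 33% of the officers have completed participation in the study (22 in each group"). An independent programmer prepares and freezes the dataset. The section then makes three statements in sequence:

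1. On display: "To ensure the double blinding of the study the subjects will not be presented in the assigned groups".
2. On who does the estimating: "The blinded statistician will estimate the overall proportion of PTS positive subjects in each group".
3. On the test: "Then one-sided Fisher's exact test will be used to compare the proportion of subjects with PTS positive in ZNS group" with that in the placebo group. The one-sided p is converted to z = Φ⁻¹(1 − p).

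The boundary follows: "With 33% information, the trial would be stopped for futility if the interim z-value" is 0.5233 or lower, described as conditional power below 10%.

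Protocol 12.4 has the same masking and blinded-statistician wording and the same z boundary. It names no test, and it describes the boundary as p = 0.60, "2-sided) corresponding to a conditional power less than 10"%.

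On access to assignments, SAP 2.5 says: "Only the pharmacist who will prepare the study drug kits and the unblinded statistician will have access to the kit assignments". SAP 9 gives the unblinded statistician no task. The direction of the alternative, ZNS proportion lower than placebo, is set in SAP 3.2.

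**The concern.** The statements do not fit together. If officers are not shown by group, a proportion in each group cannot be estimated. If the person doing the estimating is blinded, a one-sided comparison of ZNS with placebo cannot follow from that person's work. The Fisher sentence names no one, and no other role is given the comparison.

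Taken literally, staff have two choices. They can unblind a person the plan calls blinded, or they can run the look without direction. The first leaves access to unblinded efficacy results to be settled during the trial. The second changes a rule meant to stop when ZNS shows too little benefit into one that treats a trend against ZNS like a trend in its favour. The plan also does not say who receives the futility result.

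**Working it through.** **Inputs.** 22 officers per arm at the look, about one third of the information, and boundary z = 0.5233 with z = Φ⁻¹(1 − p) from one-sided Fisher (SAP 9). Final one-sided alpha 0.025, alternative ZNS lower (SAP 3.2). Design rates 50% placebo and 25% ZNS (SAP 2.7). The 60% ZNS rate used below is my illustration, not a plan figure.

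**The plan's boundary reproduces.** With t = 1/3, conditional power under the current trend is

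Φ( [z√t + (z/√t)(1 − t) − 1.96] / √(1 − t) ) = Φ( [0.302 + 0.604 − 1.96] / 0.816 ) = Φ(−1.29) = 9.8%,

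which matches the stated value below 10%. The one-sided p at z = 0.5233 is 0.300. Twice that is 0.601, which matches the protocol's 0.60. So the boundary is a point on a signed z scale, and 0.60 is that point's two-sided p.

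**The rule needs the arm labels.** Let a be the ZNS count and b the placebo count of PTS-positive officers, 22 per arm. Then p = P(X ≤ a), where X is hypergeometric with 44 officers in total, a + b positive and 22 on ZNS. For 16 positive officers out of 44:

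| ZNS | Placebo | one-sided p | z | Decision |
|---|---|---|---|---|
| 5/22 | 11/22 | 0.058 | 1.57 | continue |
| 8/22 | 8/22 | 0.623 | −0.31 | stop |
| 11/22 | 5/22 | 0.987 | −2.22 | stop |

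Pooled data do not fix z at all: all three rows have the same total. Data split into masked arms A and B leave the first and third rows indistinguishable.

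**How often the label decides.** I enumerated all 23 × 23 possible tables, weighted by binomial probabilities. No table continues under both labellings, so masked arms settle the decision only when both labellings stop.

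- At 25% ZNS v 50% placebo, both stop with probability 16.1%. The label decides the other 83.9%.
- At 50% v 50%, both stop with probability 54.9%. The label decides the other 45.1%.

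**Probability of stopping if direction were ignored.** The signed rule stops when z ≤ 0.5233. The direction-blind rule, which neither document states, stops when the larger of the two directional z values is ≤ 0.5233. Programming the protocol's figure as stop if two-sided Fisher p ≥ 0.60 gives the same probabilities.

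| True rates, ZNS v placebo | Signed rule (SAP 9) | Direction-blind rule |
|---|---|---|
| 25% v 50% (design) | 16.6% | 16.1% |
| 50% v 50% | 77.4% | 54.9% |
| 60% v 50% | 92.4% | 45.8% |

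**The case against.** The strongest reply is that the plan already contains a workable arrangement, loosely described. The blinded statistician is given only the estimate. The Fisher sentence is passive. SAP 2.5 provides an unblinded statistician, and Protocol 8.0 has the independent programmer reveal assignments in an emergency, so that role appears to have access too. The look is called sponsor-blinded, and the masking sentence could refer to subject-level displays for the study team. The rule itself is directional. The protocol's 0.60 is a correct conversion of the boundary, and a negative z still satisfies z ≤ 0.5233 and stops. The DSMB meets at least every six months, its report lists efficacy measures and any interim analysis (Protocol 11.0), and it may request unblinded data on safety issues (SAP 2.5).

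Most of this stands. A reader might infer that the rule cannot be run at all. The documents do not support that, because anyone holding the labels can compute it. A reader might also infer that the blinded statistician is told to run the Fisher test. The text names nobody. Nor do the documents support reading the direction-blind percentages as how this trial will behave, since neither document prescribes that rule.

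What does not stand is the suggestion that the roles are settled. The only statistician named for the look is called blinded, the masking sentence is not limited to the sponsor, and the person able to run the test is given nothing to do. Who sees unblinded efficacy results should be stated, not inferred.

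**Conclusion.** SAP 9 and Protocol 12.4 contradict themselves on who runs the futility look and what that person sees. This is a stated role in conflict with a stated rule, so it is wrong as written. The boundary and the SAP's directional test are not at fault.

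The practical size is conditional. If someone with the labels runs the SAP rule, nothing is lost except clarity about the blind. Only if the look were run on masked A/B arms, or with the two-sided 0.60 programmed as the rule, would stopping fall from 77% to 55% under no effect and from 92% to 46% at 60% ZNS v 50% placebo. At the design effect it is 16% to 17% either way. These figures assume exactly 22 evaluable officers per arm and independent binomial outcomes.

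A futility-only look does not inflate type I error, and the final one-sided 0.025 test is unchanged, so the primary result is not invalidated. Severity: should fix.

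**What to change.** In SAP 9 and Protocol 12.4:

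- Replace the blinded statistician with the unblinded statistician already named in SAP 2.5, and give that person both the estimates and the test.
- Limit the sentence on not presenting officers by assigned group to what the sponsor, investigators and blinded team see.
- Copy the SAP's one-sided Fisher-to-z rule, with ZNS lower than placebo as the direction, into Protocol 12.4. Remove the two-sided p of 0.60 there or mark it as descriptive only.
- State that only stop or continue is released, through the DSMB, and that no arm-level figures reach the sponsor, investigators or blinded statistician.

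The cost is a wording amendment to both documents. The role already exists, and the sample size, boundary, timing and data collection do not change.

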#### **Primary analysis.**

Frequency and relative frequency will be used to describe the distribution of the primary outcome measure in each study group. To assess efficacy, Fisher's exact test will be used to compare the proportion of officers with PTS positive in ZNS group with the proportion of officers with PTS positive in the placebo group.

To provide an estimate of treatment effect a supportive logistic regression analysis will be done with covariates: age, pre-existing hearing loss dichotomized to normal to minimal hearing loss and slight to mild loss, noise exposure history dichotomized to high risk and low risk, average post-shooting

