### 12.3 Sample size estimation

#### Sample size estimation for primary outcome measure.

Calculation of sample size for this study is based on a balanced design and a one-sided significance level of 0.025. We estimate that among officers identified as being at high risk for permanent hearing loss due to having TTS, the proportion of PTS positive officers 30 days (+/- 3 days) after shooting will be 50%. This is the proportion of PTS positive we expect to observe in the placebo group. Thus, for the primary outcome, we estimated that 66 subjects per group will provide us with 80.5% power to detect a 50% reduction in the proportion of PTS positive officers (from 50% to 25%) at the 1-sided alpha level of 0.025 and with 84% power to detect a 50% reduction in the proportion of PTS positive officers (from 50% to 25%) at the one-sided alpha level of 0.025. Our one-sided hypothesis is supported by animal studies, and lack of any evidence of hearing loss as a side effect of ZNS in human studies. A total of 132 subjects will be enrolled.

Using a number needed to treat estimate for the assumed proportion of officers with PTS positive in each study group, the absolute risk reduction of 25% tells us that we will need to treat 4 officers with TTS with ZNS to protect 1 from PTS. We do not expect to have any missing data in this short-term study, so no plan for missing data analysis is included.

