2.7 Sample Size Determination for The Primary Efficacy Outcome Measure

Calculation of sample size for this study is based on a balanced design and a one-sided significance level of 0.025. We estimate that among officers identified as being at high risk for permanent hearing loss due to having TTS, the proportion of PTS positive officers 30 days (+/- 3 days) after shooting will be 50%. This is the proportion of PTS positive officers we expect to observe in the placebo group. Thus, for the primary outcome, we estimated that 66 officers per group will provide us with 80.5% power to detect a 50% reduction in the proportion of PTS positive officers (from 50% to 25%) at the 1-sided alpha level of 0.025. A planned total of 132 subjects is to be enrolled and randomized.

We will make all the needed efforts to eliminate drop outs, and due to short term-follow-up of the study subjects in a period we do not expect any drop-outs or lost to follow-up.

All sample size calculations were carried out using PROC POWER procedure in SAS 9.4.

3 Study Outcomes

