7.1.1 Analysis of primary outcome variable

Efficacy analysis at the end of the study

The primary outcome measure for assessing effectiveness of ZNS (100 mg PO) post-shooting compared to the placebo group will be the proportion of officers with TTS defined as PTS positive 30 days (+/- 3 days) after shooting range exposure.

Audiogram will be performed to look for PTS. Officers for whom the difference at any frequency from 2-6 kHz in hearing thresholds (30 days (+/- 3 days) post-shooting - Baseline) is ≥ 10 dB HL will be defined as PTS positive. Primary analysis and sensitivity analyses will be carried out on the primary endpoint.

Primary analysis

Frequency and relative frequency will be used to describe the distribution of the primary outcome measure in each study group. To assess efficacy, Fisher's exact test will be used to compare the proportion of officers with PTS positive in ZNS group with the proportion of officers with PTS positive in the placebo group.

The confidence intervals will be calculated using method 10 described by Newcombe RG, 1998 and also described by Altman et al.

1. Altman, Douglas, et al., eds. Statistics with confidence: confidence intervals and statistical guidelines. <https://www.amazon.com/Statistics-Confidence-Intervals-Statistical-Guidelines/dp/0727913751>

Let n_1 be the number of participants in placebo group, and r_1 the number of participants with PTS in the placebo group. $p_1=r_1/n_1$ be the proportion of PTS in the placebo group, and q_1 the proportion of participants that do not have PTS in placebo group.

l_1 and u_1 are the lower and upper limits of the $100(1-\alpha)\%$ confidence interval for p_1

Using Wilson method we calculate:

$$A_1 = 2r_1 + z^2$$

$$B_1 = z\sqrt{z^2 + 4r_1 q_1}$$

$$C_1 = 2(n_1 + z^2)$$

$$l_1 = \frac{(A_1 - B_1)}{C_1} \quad u_1 = \frac{(A_1 + B_1)}{C_1}$$

z_α = the $100(1 - \alpha)^{th}$ percentile of the standard Normal distribution.

Let n_2 be the number of participants in ZNS group, and r_2 the number of participants with PTS in the ZNS group. $p_2 = r_2/n_2$ be the proportion of PTS in the ZNS group, and q_2 the proportion of participants that do not have PTS in ZNS group.

l_2 and u_2 are the lower and upper limits of the $100(1-\alpha)\%$ confidence interval for p_2

$$A_2 = 2r_2 + z^2$$

$$B_2 = z\sqrt{z^2 + 4r_2q_2}$$

$$C_2 = 2(n_2 + z^2)$$

$$l_2 = \frac{(A_2 - B_2)}{C_2} \quad u_2 = \frac{(A_2 + B_2)}{C_2}$$

The proportion difference between groups is: $D = p_1 - p_2$

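### The stated 79.4% overall power does not belong to the Fisher design specified: that design has 72.8% power and a 16.6% chance of a futility stop at the planned effect

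*SAP*

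**What the plan says.** **Final analysis.** Both documents name Fisher's exact test for the primary comparison. Protocol 12.2.1 reads: "To assess efficacy, Fisher's exact test will be used to compare the proportion of officers with PTS positive in ZNS group". SAP 7.1.1 says the same: "Fisher's exact test will be used to compare the proportion of officers with PTS positive in ZNS group". SAP 3.2 sets the level at one-sided 0.025.

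**Fixed-design power.** SAP 2.7 states that "66 officers per group will provide us with 80.5% power" for 50% versus 25%. Protocol 12.3 also states that "66 subjects per group will provide us with 80.5% power", and the same sentence goes on "with 84% power to detect a 50% reduction in the proportion of PTS positive officers (from 50% to 25%) at the one-sided alpha level". The group size, effect and alpha are the same for both figures, and nothing explains the difference.

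**Interim look.** It takes place at 22 per group. SAP 9 specifies a one-sided Fisher test, whose p-value "from Fisher's Exact Test will be converted to a z-value using the inverse Normal transformation". The trial stops for futility if z ≤ 0.5233. Protocol 12.4 gives the same cut, adds that it is p = 0.60 ("2-sided) corresponding to a conditional power less than 10" percent), and names no interim test. Both sections then state: "This design would provide 79.4% overall power".

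**The concern.** The SAP gives 80.5% without the look and 79.4% with it, an implied cost of 80.5 − 79.4 = 1.1 points. That is too little for a cut well above zero at one-third of the information. Fisher's test at 22 per group is also conservative, so converting its p-value to z makes the stop easier to trigger than the nominal cut suggests.

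The SAP is shared with the DSMB, and Protocol section 11 lists early stopping rules and power or interim analysis among the contents of the DSMB report. Someone deciding whether the rule is acceptable would think it almost free. If the true cost is much larger, they are accepting a sizeable chance of abandoning a drug that works as hoped.

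**Working it through.** **Inputs, all from the documents**
- PTS-positive rates of 50% (placebo) and 25% (ZNS), 66 per group, no dropout: SAP 2.7
- 1:1 allocation: SAP 2.4
- One-sided alpha 0.025: SAP 3.2
- Final test Fisher: SAP 7.1.1
- Interim at 22 per group, one-sided Fisher p, z = Φ⁻¹(1 − p), stop if z ≤ 0.5233: SAP 9

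**Step 1. Reproduce the plan's own figures**
- Fixed-design 80.5%: the Walters arcsine approximation to Fisher power gives 80.53% at 66 per group. Exact Fisher power is 81.3%. The 80.5% is therefore a Fisher figure.
- Boundary: at 33% information, z = 0.5233 gives current-trend conditional power of 10.0%, as stated. The one-sided p at the cut is 1 − Φ(0.5233) = 0.3004, or 0.60 two-sided, as Protocol 12.4 prints.
- Overall 79.4%: this is approached only with tests the plan does not name. Pooled z at both looks gives 79.1% by normal approximation and 80.4% exactly. Mid-p at both looks gives 79.5%.

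**Step 2. The design as specified, exactly**

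Let (c, t) be the placebo and ZNS positives at the interim, with c ~ Bin(22, 0.50) and t ~ Bin(22, 0.25). Let c′ ~ Bin(44, 0.50) and t′ ~ Bin(44, 0.25) be those that follow.
- P(stop) = Σ P(c, t) over tables with z(c, t) ≤ 0.5233
- Overall power = Σ P(c, t) · P(Fisher p at (c + c′, t + t′) < 0.025) over the remaining tables

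Results:
- P(stop) = 0.1664
- Overall power = 0.7284
- Shortfall = 79.4 − 72.8 = 6.6 points

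A simulation of 1,000,000 trials agrees (stop 0.1663, power 0.7289). Reading the cut as a two-sided Fisher p of 0.60 gives the same stopped tables and the same power.

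In counts, with 1 to 14 ZNS positives among 22 the trial continues only if placebo has at least 3 more. For example, 8 versus 6 gives p = 0.373, z = 0.32, stop; 9 versus 6 gives p = 0.263, z = 0.63, continue.

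**Step 3. Cost of the look**
- Power lost: 0.8133 − 0.7284 = 0.0849, or 8.5 points
- Share of stopped trials that would have been significant at 66 per group: 0.0849 / 0.1664 = 51%
- Type II error: 1 − 0.728 = 27%, against the stated 1 − 0.794 = 21%

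**Step 4. Consistency with the documents' own fixed powers (normal theory)**

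Let θ = 1.96 + Φ⁻¹(fixed power). The interim Z₁ has mean θ√(1/3), the final Z₂ has mean θ, and their correlation is √(1/3). Overall power = P(Z₁ > 0.5233 and Z₂ > 1.96).

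| Fixed power | θ | P(stop) | Overall power |
|---|---|---|---|
| 80.5% | 2.820 | 13.5% | 74.2% |
| 84% | 2.954 | 11.9% | 77.9% |

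Finishing at 79.4% would need a fixed power of 85.4%, above both printed values.

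**Step 5. Other combinations, exact**

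| Interim test | Final test | Overall power |
|---|---|---|
| Fisher | Fisher (as specified) | 72.8% |
| Fisher | pooled z | 75.8% |
| pooled z | Fisher | 77.0% |
| mid-p | mid-p | 79.5% |
| pooled z | pooled z | 80.4% |

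Every combination in the table that keeps Fisher at either look falls short of 79.4%.

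**The case against.** The strongest reply is that 79.4% is a sound figure attached to the wrong test. Mid-p at both looks has a fixed power of 84.4% and an overall power of 79.5%, close to the protocol's 84% and 79.4% taken as a pair. On that view the slip may lie in the word Fisher in SAP 9 rather than in the power, and deleting the 84% picks one way of reconciling the two. This stands as a possible origin, and the documents do not say how either figure was obtained. It does not rescue the statement. Neither document mentions mid-p or z tests for this comparison, both name Fisher for the final analysis, and a Fisher final test gives at most 77.0% in the combinations above.

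A second reply is that the actions only may be taken, so the stop is not binding. If the rule were ignored, power would be up to 81.3%. But the plan defines overall power as including passage through the look, and 79.4% is not the non-binding figure either.

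Third, the trial would run identically after the edit, since the rule, tests and sample size do not change. That is true. The defect is a wrong operating characteristic, not an invalid test, and no passage makes 79.4% itself a decision input.

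**Conclusion.** The concern holds. For the design as written, overall power is 72.8%, not 79.4%, and the probability of a futility stop at the planned effect is 16.6%, which the documents do not state. The look costs 8.5 points of power. Type I error is not inflated, because the only early stop is for futility, and the final test and estimate are unaffected.

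Protocol 12.3 also gives two powers for one design. The 80.5% agrees with Fisher and is the only figure in the SAP; a conventional Fisher test does not give 84%.

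The result assumes rates of 50% and 25%, exactly 22 then 66 evaluable officers per group, no missing outcomes, and a stop that is followed whenever z ≤ 0.5233. That an approximate or mid-p calculation produced the 79.4% is inference.

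**What to change.** - **SAP 9 and Protocol 12.4:** restate overall power as about 73% and add the probability of a futility stop at the planned effect, about 17%.
- **Protocol 12.4:** name the interim test (one-sided Fisher, p converted to z) so that it matches SAP 9.
- **Protocol 12.3:** delete the 84% clause and leave 80.5%, as in SAP 2.7.

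The cost is wording in three sections. It needs no extra officers and no change of test or boundary. The downside is a less favourable stated power. A less conservative interim statistic or final test would recover some power, but that is a separate design choice and is not needed to correct the statement.
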